733 report + macroscopic image and for text report + dermoscopic image. We will calculate percentage
734 agreement and kappa statistics across diagnostic categories and 95% confidence intervals for
735 these.

736

737 *Costing study*

738 We will identify, measure and value all resources used (micro-costing approach) to estimate the
739 total costs to patients, to the health system, and to the planet (carbon emissions) for the
740 intervention and control groups. All costs associated with SSE, skin surveillance and management

741 of newly identified lesions, out of-pocket costs, opportunity costs and carbon costs will be
742 included.²⁰

743 Patient diaries

744 Patient out-of-pocket and health system costs associated with each arm of the trial will be
745 estimated using a monthly resource use diary.^{21,22} The diary will be used to document and measure
746 health behaviours and service use - such as hospitalisation, other allied health consultations, use of
747 alternative therapies and self-monitoring behaviours. The diary will also record any melanoma
748 follow up consultations and procedures conducted by other providers (e.g. GPs). We will ask
749 patients to report the number of trips made to their melanoma follow-up clinic and the mode of
750 transport used. We will also ask patients to report any visits to other physicians in the community
751 for a skin lesion excision or other skin cancer related procedures. The time each patient spent to
752 perform digital SSE and to attend follow-up visits will be recorded. The diary will also document
753 carers' days out-of-role (including paid and unpaid work), travel costs and direct carer costs.

754 Review of medical records

755 All recorded melanoma follow up consultations and procedures will be extracted from the patients'
756 medical records in the clinic databases. We will also extract all diagnostic tests during the trial
757 period.

758 The mean (and standard deviation) volume of resource use by category and mean cost per
759 participant will be tabulated. The difference in resource use and costs between the intervention and
760 control groups will be presented with 95% CIs, and P- values for differences will be calculated by
761 two sample t-tests.

762 Carbon Costs

763 We will then apply a carbon value to each of the types of resource use identified above. This will
764 include direct estimation (e.g. travel) and indirect (e.g. life cycle costs of a tablet/smartphone). We
765 will do this using data from the Australian Industrial Ecology Virtual Laboratory (IELab), which offers
766 a unique platform for the compilation of customized economic input-output tables for the Australian
767 economy. As a first step, we will couple these economic tables with data on carbon emissions for
768 every economic sector. Next, we'll use these integrated tables to undertake well-established input-
769 output mathematical calculations to estimate the direct impacts, as well as the indirect impacts
770 throughout the infinite supply chains of a product, for example. As opposed to conventional life
771 cycle assessments that are affected by so-called truncation errors because they only take into
772 account selected supply chains, input-output analysis considers the entire supply chain of a
773 product, technology or an organization in question, and this provides a complete picture of the
774 impacts.

776 **Qualitative sub-study (intervention group only)**

777 We will conduct a qualitative evaluation after the 6 month follow up among a sub-sample of patients
778 and clinicians. We will invite participants who were randomised to the intervention to indicate their
779 interest in taking part in a interview (number of participants=30) to explore in depth their
780 experiences with digitally supported self-examination. We will carry out face-to-face or telephone
781 interviews among these patients at 6 months after randomisation. Interviews will be audio recorded
782 and transcribed verbatim. We will also interview participating clinicians (n=5-10) to explore their
783 experience of the benefits and limitations of the intervention. The study will take a
784 Phenomenological perspective and will use Framework Analysis,²³ a matrix based method of
785 thematic analysis which has been used successfully in numerous screening studies.^{24,25}

786 **13.6. Missing data**

787 Missing data will be imputed in analysis as appropriate.

788 **13.7. Deviations from original statistical plan**

789 The version of this document and the statistical analyses plan will be updated with each change,
790 and each change noted.

791

792 **14. Responsibilities of the Principal Investigator at each site**

793

794 The study will be performed in accordance with the CPMP/ICH Note for Guidance on Good Clinical
795 Practice (CPMP/ICH/135/95) in Australia and applicable guidelines in participating sites overseas.

796

797 The study protocol, including the final version of the participant information and informed consent
798 form to be used, must be approved by the Trial Management Committee and a constituted Human
799 Research Ethics Committee (HREC) prior to enrolment of any patients into the study. The opinion
800 of the HREC should be dated and given in writing. It is the responsibility of the PI at each site to
801 forward a copy of the approval from the HREC clearly identifying the protocol submitted for review
802 and a copy of the approved participant information sheet and consent form to the Trial Coordinating
803 Centre prior to entry of patients.

804

805 The investigator is responsible for ensuring that written informed consent by the patient is obtained
806 before study entry. The investigator is responsible for informing the Trial Coordinating centre and
807 the HREC of any SAEs and/or major amendments to the protocol as per local requirements.

808

809 The investigator is responsible for ensuring that all regulatory requirements are followed.

810

811 The investigator is required to ensure compliance with the protocol in its entirety. It is the
812 responsibility of the investigator to maintain adequate and accurate CRFs.

813

814 **15. Reporting of Results**

815

816 The Study Chair and TMC will be responsible for decisions regarding presentations and
817 publications arising from this study.

818

819 Authorship credit should be based on the Vancouver statement by the International Committee of
820 Medical Journal Editors, i.e. substantial contribution to all three of the following criteria:

- 821 • Conception and design OR analysis and interpretation
- 822 • Drafting article OR critically revising it for intellectual content
- 823 • Final approval of version to be published

824 Or, a fourth criterion is:

- 825 • Contributors who register 5% or more (accrual by institution) of the evaluable cases on a
826 study will be listed as authors. The designated author is the choice of the institution's PI and
827 in most cases would be the investigator with the highest accrual. If an institution places a
828 large number of cases on the study, that institution will get an additional author for every 10%
829 of the participants accrued, not to exceed a total of three authors (i.e. two authors for $\geq 15\%$
830 accrual and three authors for $\geq 25\%$ accrual)

831

832 Acknowledgement of the collaboration between MASC Trials is required in all publications,
833 abstracts and presentations. Publications and abstracts must be presented to the Study Chair and
834 TMC for review and approved prior to submission. Draft publications will be presented to the
835 Publications/Writing Committee of each collaborating group for comment prior to submission.

836

837 Publications must be reviewed by the MASC Trials Executive Committee prior to submission.

838

839 16. Quality Assurance

840 16.1. Data Management and Source Data Verification

841 Trial sites are expected to regularly provide the completed CRFs reflecting the patient visits to the
842 Trial Coordinating Centre. Copies of relevant documents for source verification and quality
843 assurance will be requested including various imaging scans and reports.

844
845 The Trial Coordinating Centre will issue data queries as required to clarify CRF data and will report
846 to the Study Chair regarding CRF submission and query completion rates as well as any issues
847 related to protocol compliance.

848 16.2. Protocol Amendments

849 Changes and amendments to the protocol can only be made by the TMC. Approval of amendments
850 by the HREC is required prior to their implementation. In some instances, an amendment may
851 require a change to the participant information sheet and/or consent form. The Investigator must
852 receive approval/advice of the revised consent form prior to implementation of the change. In
853 addition, changes to the CRFs, if required, will be incorporated in the amendment.

854 16.3. On Site Monitoring

855 Site monitoring is scheduled annually for this study (also subject to funding and recruitment rate
856 and at the discretion of the TMC).

857 16.4. Site Audits

858 This study is subject to audit by each of the groups involved and could occur at any stage of the
859 study. Sites will be informed in advance in writing, outlining and the scope of the audit should one
860 occur.

861 16.5. Confidentiality

862 The study will be conducted in accordance with applicable Privacy Acts and Regulations. All data
863 generated in this study will remain confidential. All information will be stored and backed-up
864 securely at the MASC Trials Coordinating Centre or at the School of Public Health at University of
865 Sydney and will only be available to staff directly involved with the study. Hard-copy documents will

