408 Participants allocated to the intervention will receive:

- 409 • An educational booklet 'Your guide to early melanoma',
- 410 • Web-based ASICA skin checker log-in. The web-based ASICA skin checker combines
411 instructional videos, guided total skin self-examination and electronic reporting,¹⁵
- 412 • A dermatoscope to attach to their phone similar to that reported in *Manahan et al.*¹⁶.
- 413 • Detailed written instructions on how to use the smartphone App and dermatoscope.

- 414 • Video outlining how to use the dermatoscope and associated App/online submission
 415 platform.
 416 • Email or SMS text reminders every 2 months to perform SSE.
 417 • Teledermoscopy: participants are required to take dermoscopic images of at least 3 lesions
 418 and up to 9 lesions on each SSE, including all lesions that concern them, and submit these
 419 through the smartphone App. They are also required to enter a text description of the results
 420 of SSE for each part of the body and submit this through the web-based ASICA skin
 421 checker. Both dermoscopic images and text reports will be sent securely to one of the study
 422 dermatologists, who will undertake teledermatology review within 3 days and feedback the
 423 results to the participant.
 424 • Unscheduled visits as needed in addition to those prompted through Teledermatology.
 425 • Scheduled visits as per treating clinician.
 426

427 Those allocated to the control arm will receive:

- 428 • An educational booklet 'Your guide to early melanoma';
 429 • Unscheduled visits as needed
 430 • Scheduled visits as per treating clinician
 431

432 All participants will receive two study questionnaires; one at baseline and one at 6 months.
 433

434 **8.4. Blinding**

435 Blinding of participants, site staff and treating clinicians will not be possible in this trial. Where
 436 possible, outcome assessment will be done masked to study group allocation.
 437

438 **8.5. Duration of treatment/ Study**

439 Unless the study is closed prematurely, it will proceed to the pre-defined accrual target. Following
 440 announcement of closure to recruitment by the research team, no further enrolment will be
 441 possible. It is anticipated, based on estimates from individual sites that the accrual target will be
 442 reached over a period of 6 months. Each participant will be followed up for 6 months. The timeline
 443 below provides an outline of anticipated study milestones:
 444
 445

Timeline	2017	2018	2019	2020

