566

567 **10.2. Intervention/ treatment modification**

568 Participation in this study does not stop participants in either the intervention or control groups from
569 seeking professional medical care. Access to formal health services will, however, be recorded as
570 part of the study.

571 **10.3. Distribution, packaging and labelling**

572 The initial Invitation letter will be sent on clinician letterhead to the participant at the address on file
573 at the clinic database. Following consent and receipt of the baseline study questionnaire, the study
574 packages will be distributed by the research coordinator, according to their random intervention or
575 control group allocation, to participants through the mail or during their routine clinic visit (as
576 directed by participant preference).

577 **10.4. Accountability for intervention**

578 It is the responsibility of the research coordinator to make sure that all participants receive their
579 packages according to their randomised group allocation.

580 **11. Safety Reporting**

581 **11.1. Adverse Events**

582 An Adverse Event (AE) can be any unfavourable and unintended sign, symptom, or disease
583 temporally associated with the use of an intervention, whether or not related to the intervention.

584
585 In cases of surgical or diagnostic procedures, the condition/illness leading to such a procedure is
586 considered as the AE rather than the procedure itself.

587

588 Medical device adverse event / incident:

- 589 • An event associated (caused or partially attributable) with the use (or misuse) of a
590 medical device.
591 • An event that resulted in or could have resulted in (had effective intervention not taken
592 place) serious injury, illness or death to patient, healthcare worker or other person.
593 • Faults that may affect the quality of device, timeliness of assessment and cost-
594 effectiveness such as, problems with getting the device to operate, repeated repairs,
595 device design and difficulty of use.
596

597 All AEs with the smartphone App and dermatoscope will be recorded and reviewed by the trial
598 management committee.
599

600 **11.2. Serious Adverse Events**

601 **SAE Definitions**

602 A serious adverse event (SAE) is any untoward medical occurrence which:

- 603 • is fatal;
604 • is life-threatening;
605 • requires unanticipated in-patient hospitalisation or prolongation of hospitalisation;
606 • results in persistent or significant disability or incapacity;

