607 • is a congenital anomaly/birth defect;
608 • is a grade 4 (NCI CTCAE v4.0) toxicity;

609 **and**

- 610 • could be related to the device and/or software
 611 The term “life threatening” in the definition of SAE refers to an event in which the participant was at
 612 risk of death at the time of the event; it does not refer to an event which, hypothetically, might have
 613 caused death if it were more severe.

614

615 **SAE Reporting**

616 All relevant and subsequent information relating to each reported SAE must be submitted on the
 617 CRF, along with any available source documentation, to the Trial Coordinating Centre. This must
 618 be completed within 24 hours of the site becoming aware of the event and all SAE CRFs require
 619 the signature of the Principal Investigator.

620

621 **SAE Reporting Timelines**

Type	Timeframe
Initial SAE Report	The site must submit the original SAE Form to the Trial Coordinating Centre within 24 hours of becoming aware of a trial participant experiencing an SAE. Please provide copies of relevant source documents if available. Should the site have any questions please immediately contact the Trial Coordinating Centre for assistance.
Updated Report	The site should provide any updates to the Trial Coordinating Centre as soon as possible. Please use the original SAE Form, and use additional Forms if more space is required. Please provide copies of all relevant source documents if available.
Completed Report	Once the event has resolved or if the participant has died, using the original SAE Form(s), the site should provide the complete report to the Trial Coordinating Centre as soon as possible. This must include relevant source documents.

622

623 All SAEs will be reviewed by the Study Chair and also summarised for review by the Data Safety
 624 Management Committee.

625

626 SAEs will be reported as per the local Ethics Committee (EC)/Research Governance Officer (RGO), in
 627 accordance with international and local laws and regulations.

628

629 Should any trial site have any questions they will immediately contact the Trial Coordinating Centre for
 630 assistance.

631 **12. Outcomes/ Measures**632 **12.1. Primary outcome**

633 **(M1)** The primary outcome is the **proportion of patients who are invited to participate who are**
 634 **finally randomised into the trial.**

635 **12.2. Secondary outcomes**636 **(M2) Skin –Self Examination (SSE) including:**

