665 (including paid and unpaid work), travel costs and carer costs. The diary will be based on existing
666 resource use questionnaires resource use recorded in databases.

667 **(M9) Qualitative results:** We will carry out face-to-face or telephone interviews with a sub-set of
668 intervention group participants at 6 months after randomisation to explore in depth patients'
669 experiences with digitally supported self-examination. We will also interview clinicians to explore
670 their experience of the benefits and limitations of the intervention.

671 **12.3. Potential confounders and biases**

672 **(M10) Demographic and other risk factors including:**

673 Age, sex, ethnicity, Indigenous status, language spoken, marital status, children, occupation,
674 income, highest education level, postcode/SEIFA, brand of smartphone owned (if applicable),
675 baseline use of digital technology/ internet, and personal history of depression or anxiety. We will
676 collect these data using standardised items from the Australian Census questionnaire and other
677 instruments, where appropriate.

678 Clinical characteristics of the index melanoma including AJCC sub-stage and site, retrieved from
679 administrative datasets at the clinics.

680 **13. Statistical methods**

681 **13.1. Sample size and justification**

682 A sample size of 100 participants, with 1:1 allocation to intervention vs control groups, will ensure
683 that the 95% confidence interval for the proportion of potential participants who are recruited has a
684 margin of error of <10% (assuming that 30% of contacted, eligible participants are recruited).

685
686 A sample size of 30 participants in the qualitative sub-study is a well-accepted sample size in
687 qualitative studies using in-depth interviews.¹⁸
688

689 **13.2. Feasibility**

690 Administrative data from our main clinic (MIA) indicates that approximately 800-900 patients are
691 treated for localised melanoma at MIA each year and approximately 50% then attend regular
692 follow-up at MIA.¹⁹ Recruiting 100 patients over 6 months from all patients treated for localised
693 melanoma who are attending follow-up at MIA and the clinic in Newcastle, is highly feasible.

694

695 13.3. Early stopping

696 There are no safety endpoints or criteria for early study termination.

697

698 13.4. Analyses plan**699 13.4.1. Statistical analysis for primary endpoint**

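### SAE status requires a possible link to the device or software, so SAE and AE rates cannot be compared between arms and the safety committee's summary is one-sided

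*Combined protocol and SAP*

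**What the plan says.** **Adverse events (Section 11.1).** An AE is an unfavourable event "temporally associated with the use of an intervention, whether or not related to the intervention". The device-incident list that follows is broad. It includes "An event associated (caused or partially attributable) with the use (or misuse) of a" medical device, and it also covers faults bearing on how promptly an assessment is made. The only recording commitment is narrower: "All AEs with the smartphone App and dermatoscope will be recorded and reviewed by the trial" management committee.

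**Serious adverse events (Section 11.2).** Six seriousness criteria are listed, from fatal events to the last, "is a grade 4 (NCI CTCAE v4.0) toxicity". A separate, emphasised 'and' then adds the condition that the event "could be related to the device and/or software". The site must submit the SAE form within 24 hours of becoming aware of the event. SAEs are reviewed by the Study Chair and summarised for the safety committee.

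**Who has the device (Sections 8.3 and 10.1).** The dermatoscope, the App and the ASICA log-in are listed for the intervention arm only. Controls get the booklet, visits and monthly diaries.

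**Blinding (Section 8.4).** Site staff and treating clinicians are not blinded.

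**Early stopping (Section 13.3).** "There are no safety endpoints or criteria for early study termination".

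**The concern.** Seriousness and causality are separate judgements. Seriousness describes what happened to the participant. Causality is an opinion about why. When causality is part of the definition, an event judged unrelated is not an SAE at all, so it does not reach the summary that the safety committee reads. The site has to make that judgement before it files the form, and it knows the allocation.

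Two things are at stake. First, there is no control count against which to read the intervention count. Section 5.2 says the pilot supports planning of a larger trial that aims to show health outcomes no worse than under clinician-led surveillance. A background serious-event rate, and a tested way of collecting it in both arms, are things a pilot can usefully supply.

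Second, Section 11.2 names the device and the software but not the dermatologist's recommendation. If a lesion is rated No Concern Today and later proves malignant, sites have no rule for deciding whether a resulting serious event counts. Two sites could classify the same event differently.

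**Working it through.** The plan gives no figure on this point to reproduce. The check is a reading of the sections against each other, followed by arithmetic on scale.

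**1. Is relatedness part of the definition?** Yes. It is joined by 'and' to the seriousness list in 11.2, not placed in the reporting timelines. It decides what is an SAE, not only how fast one is reported.

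**2. Do 11.1 and 11.2 agree?** No. The 11.1 definition ignores relatedness, the 11.1 recording sentence covers only the App and dermatoscope, and 11.2 requires possible relatedness.

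**3. Can a control event qualify?** In effect no. Controls are not given the device or software (8.3, 10.1), so a control death or admission has nothing to be related to. That is 50 of 100 participants (Section 3).

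**4. Does harm after a false reassurance qualify?** The text does not settle it. The report is a human judgement, but it rests on images taken with the dermatoscope and sent through the App.

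**5. What is collected in both arms by other routes?**

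| Item | Where | Sent to the safety committee? |
|---|---|---|
| Death, with reason | 8.6.2 | Not stated |
| Surgical procedures, histopathology | 8.6 | Not stated |
| Hospitalisation | Diary, 12.2 (M8) and 13.5 | Not stated |
| Fear of recurrence, DASS-21 | 12.2 (M3, M4) | Not stated |

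**6. Does any analysis set teledermatology ratings against pathology?** None is listed. The repeatability sub-study (13.5) measures agreement among dermatologists. Lesions surgically evaluated (12.2) is a count.

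**7. Scale.** The documents give no serious-event risk, so a 6-month risk p of 1% to 10% is assumed.

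- Expected control participants with an uncounted event: 50 × p.
- Chance of at least one: 1 − (1 − p)^50.
- Power at 50 per arm to detect a doubling (p₁ = p, p₂ = 2p, d = p, p̄ = 1.5p, two-sided 5%): Φ{[d − 1.96√(2p̄(1−p̄)/50)] / √([p₁(1−p₁) + p₂(1−p₂)]/50)}.
- n per arm for 80% power: [1.96√(2p̄(1−p̄)) + 0.842√(p₁(1−p₁) + p₂(1−p₂))]² / d².

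| Assumed p | Expected in 50 controls | Chance of ≥1 | Power for doubling | n per arm, 80% power |
|---|---|---|---|---|
| 1% | 0.5 | 39% | 6% | 2319 |
| 2% | 1 | 64% | 8% | 1141 |
| 5% | 2.5 | 92% | 15% | 435 |
| 10% | 5 | 99% | 29% | 199 |

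For zero events in one arm of 50, the exact upper limit is 1 − 0.05^(1/50) = 5.8% (one-sided 95%) or 1 − 0.025^(1/50) = 7.1% (two-sided 95%). These limits and the power column describe what 50 per arm can support once both arms are recorded. They do not measure the defect.

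**The case against.** The strongest reply is that this is a feasibility pilot whose primary outcome is the proportion randomised, that the intervention is added to usual scheduled follow-up, and that a No Concern Today report tells the patient to have the lesion reviewed at the next scheduled visit. With 6% to 29% power under the assumed risks, the arms could not be tested on serious events anyway. The statement in 13.3 also sits under early stopping and can be read as concerning termination only. All of this stands. It lowers the weight of the point but does not justify recording events on one side only.

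Two stronger readings are tempting, and the documents do not support them.

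- *Harm from a wrongly reassuring report can never be an SAE.* A possible link is a low bar, and 11.1 accepts partial attribution and misuse, so such an event is left undefined, not excluded. The relatedness clause is also often not the obstacle: a melanoma found later and simply excised would often fail the seriousness list first.
- *The arms cannot be compared on safety at all.* Deaths with cause, procedures, histopathology, hospitalisation and psychological scores are gathered in both arms, and 10.2 says use of formal health services will be recorded. What cannot be compared is SAE and AE rates.

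The blinded re-reading in the repeatability sub-study also gives some information on reader error. It takes place after close-out, however, and the planned analysis measures agreement, not correctness.

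**Conclusion.** The point holds in this limited form. Relatedness is built into the SAE definition, and AE recording is confined to the App and dermatoscope, so the 50 control participants are in effect outside both systems. SAE and AE rates cannot be compared between arms, and the committee's SAE summary is one-sided. Whether harm after a falsely reassuring report counts is unclear. The both-arm data that could fill the gap are not routed to the committee, and no analysis links ratings to pathology.

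If 1% to 10% of controls had a serious event in 6 months, 0.5 to 5 control participants with events would be expected to go uncounted as SAEs. That range is an assumption. Two readings also matter: that controls have no access to the study device or software, and that the site decides on relatedness, which follows from its duty to file the form but is not stated outright.

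The pilot's primary result is unaffected. This is a cheap improvement.

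**What to change.** 1. In 11.2, remove the relatedness condition from the SAE definition. Bring the AE definition and the recording sentence in 11.1 into line with each other and with 11.2.
2. Record events meeting a seriousness criterion in both arms. Add separate relatedness fields for the device, the software and the teledermatology recommendation. Relatedness may still decide which events get expedited reporting.
3. Give the safety committee the serious events by arm, including deaths and hospitalisations already captured elsewhere.
4. Add to 13.5 a descriptive table of any melanoma confirmed in a lesion earlier rated No Concern Today or Follow Up Photo, using the histopathology already extracted. Step 1 alone would not capture most of these. Keep the rating for each lesion so that it can be matched to the pathology. Present the table as a count, not an error rate, because only removed lesions have pathology and a lesion rated late has little follow-up.

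**Cost.** A few more event forms among 100 participants over 6 months, some lesion matching, and a short amendment to 11.1, 11.2 and 13.5. The between-arm comparison remains descriptive at 50 per arm and should be labelled so.
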